[name], Co-Investigator
Drexel University

[name], Co-Investigator
Northwestern University

[name], Co-Investigator
Drexel University

6) Objectives

This study is designed to test new approaches to supporting long-term behavior change. Specifically, this study will test whether using coaches, program peers, or family/friends as sources of support and accountability can improve long-term weight loss.

Aim 1: Test the hypotheses that Coach Share, Group Share, and Friend/Family Share will each improve long-term weight loss (primary outcome) and PA and calorie intake (secondary outcomes) (i.e., outcomes will be compared for participants who are randomized to engage in that type of data sharing partnership, versus those who are not). Exploratory analyses also will determine if effects are partially or fully additive, antagonistic, or synergistic when participants are assigned to more than one type of data sharing partnership.

Aim 2: Test the following mediators of intervention effects: perceived supportive accountability, motivation, self-regulation, self-monitoring engagement, coaching quality, social comparison, and social support.

Aim 3: Determine how quality of the relationship with the coach, group members, and friend/family member over time may differentially moderate treatment effects and predict data sharing efficacy.

7) Background

In the proposed study, adults with overweight/obesity (i.e., “index participants”) will enroll in a 24-month LM program and use digital self-monitoring tools on a daily basis (wireless body weight scale, wearable PA sensor, and app to record dietary intake). In months 1-3, groups will meet remotely every week through videoconferencing to initiate weight loss. Contact in months 4-24 will continue remotely, with group meetings continuing to be held via videoconferencing (once per quarter) and brief, individual phone calls with the coach (twice per quarter). Participants also will exchange monthly text messages with the coach; monthly text messages with a small group of fellow participants; and monthly text messages with a friend or family member outside of the program who will be trained to provide support. A factorial design will be used to efficiently test the independent effects of three types of data sharing partnerships:

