
Statistical Analysis

Descriptive statistics and exploratory graphing will be generated for all variables. Data summaries will be produced for the full sample and by condition. Continuous variables will be transformed if necessary. Baseline characteristics will be compared for each ON versus OFF contrast, as well as for each of the 8 study arms, using ANOVAs for continuous variables and a chi-square tests for categorical variables. Key baseline variables that differ by condition will be considered for use as covariates in the analyses described below. Likelihood-based estimation methods and multiple imputation models

will be used to handle missing data.

Aim 1

This study will evaluate the hypotheses that long-term weight loss (primary outcome) and PA and calorie intake (secondary outcomes) will be superior in Coach Share ON vs. OFF; in Group Share ON vs. OFF; and in Friend/Family Share ON vs. OFF. We will model the pattern of change in weight over time using multilevel models. The first level will model individual weight loss over time with baseline as time 0. At the second level, the individual intercept and slope will be entered as outcomes with each of the three types of data sharing examined separately as a predictor. The cross-level interaction between time and type of data sharing (e.g., Coach Share ON vs. OFF) will be used to determine the effect of the partnership factor on the pattern of change in weight. Restricted maximum likelihood will be used to estimate model parameters and to test the significance of random effects. Both linear and higher-order time effects will be examined. Similar multilevel models will separately examine the effect of each of the three partnerships on PA and calorie intake. As an exploratory aim, we also will test the interaction effects of the three data sharing partnerships by adding higher-order interaction terms to the aforementioned multilevel models.

Aim 2

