additional codes based on themes that arise, non-substantive codes, and detailed codes for analysis of specific topics. We will create a coding dictionary based on analysis of the first five transcripts, and every fifth subsequent transcript will be double-coded in order to assess interrater reliability. If there is <90% agreement in coding, we will re-assess domains to identify areas in which different labeling may have been used for similar ideas.

Power analyses suggest that a sample size of 238 is required for 80% power with the significant level of 0.05 and four assessment points, assuming the ratio of the variability of level-1 coefficient to the variability of level-1 residual is at least one. The study is adequately powered with the proposed sample size of 320 with up to 25% attrition.

c) **Withdrawal of Subjects**

Participants will be withdrawn from the research without their consent if there is a change in the subject's medical condition, if all or part of the study is discontinued for any reason by the sponsor, investigator, university authorities, or government agencies, new information is available to the investigator, or there are harmful unforeseen reactions experienced by the participant or other participants in the study. Participants will be notified about any new information that may affect their health, welfare, or choice to stay in the research.

If the friend/family member identified by the index participant does not consent to participate in the study, the index participant will be asked to identify another friend/family member. If they cannot find another friend/family member who would be willing to consent to the study (which is an inclusion criteria), then the index participant will be deemed ineligible and provided with relevant weight loss referrals.

Index participants and friends/family members may withdraw from the study at any time, and it will not be held against them. If an index participant or friend/family member stops being involved in the research, already collected data may not be removed from the study database. Any fee the index participant or friend/family member may be paid will be determined by the amount of time they spend in the trial and, if they do not complete the study, the reason for leaving the study early.

If termination is necessary, the project coordinator will contact the index participant or friend/family member immediately to discuss the grounds for their termination.

2) **Risks to Subjects**

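### Aim 1 tests the three randomized sharing factors in separate models; one joint model per outcome fits the factorial design better and costs almost nothing

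*Protocol*

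**What the plan says.** Section 7 (Background) of the protocol justifies the design on efficiency: "A factorial design will be used to efficiently test the independent effects of three types of data sharing partnerships". Section 6 (Objectives, Aim 1) hypothesizes that each of the three partnerships improves long-term weight loss. It also asks, as an exploratory question, whether their effects are additive, antagonistic or synergistic.

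The Statistical Analysis section, Aim 1, enters the person-level intercept and slope as outcomes "with each of the three types of data sharing examined separately as a predictor". The test is the time-by-factor term: "The cross-level interaction between time and type of data sharing (e.g., Coach Share ON vs. OFF) will be used to determine the effect". For the secondary outcomes, "Similar multilevel models will separately examine the effect of each of the three partnerships on PA and calorie intake". Factors are combined only in the exploratory step: "we also will test the interaction effects of the three data sharing partnerships by adding higher-order interaction terms to the aforementioned multilevel models". Aim 3 adds relationship quality to the Aim 1 model and so inherits its structure.

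The power paragraph at the end of that section says that "a sample size of 238 is required for 80% power" "with the significant level of 0.05 and four assessment points". It assumes that the ratio of slope variability to residual variability is at least one, and calls 320 adequate with up to 25% attrition. It gives no effect size.

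**The concern.** The natural reading is three one-factor models for each outcome. A model for Coach Share alone cannot attribute slope differences to Group Share or Friend/Family Share, so if those factors work, their effects count as unexplained variation between people. The design was chosen so that three effects could be estimated efficiently from the same participants, and this analysis gives up part of that gain exactly when the trial's own hypotheses are true. It also leaves any chance association between factors unadjusted.

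The interaction step raises a second problem. If product terms are added to a model holding only one factor, the other factors' main effects are absent. A product term can then pick up part of a main effect, which blurs the additivity question that the step is meant to answer.

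**Working it through.** **Inputs from the protocol.** Total N for 80% power is 238; alpha is 0.05; there are four assessment points; the variance ratio is at least 1; 320 are randomized with up to 25% attrition, so 320 × 0.75 = 240 are retained; allocation is 160 ON and 160 OFF on each factor.

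**Assumptions (not in the protocol).** The test is two-sided. The four occasions are equally spaced at 0, 1, 2, 3. The ratio is exactly 1 (slope variance 1, residual variance 1). The effect is a slope difference δ in slope SDs.

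**Reproducing 238.** For a two-group difference in linear slope, the noncentrality is

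λ = (N/4) × δ² / (1 + V), with V = residual variance / Σ(t − mean t)², referred to F(1, N − 2).

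Here Σ(t − 1.5)² = 2.25 + 0.25 + 0.25 + 2.25 = 5, so V = 0.20. With δ = 0.40 the smallest N reaching 80% is 238 (power 80.1%); δ = 0.38 gives 264 and δ = 0.42 gives 216. So 0.40 fits, but it is back-solved. The attrition step is right: 238 / 0.75 = 317.3, or 318, within 320.

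**Effect of leaving two factors out.** A balanced ON/OFF factor with slope effect δₒ contributes (δₒ/2)² to the between-person slope variance, so two contribute 2 × δₒ²/4. At N = 240 and δ = 0.40 the numerator of λ is 60 × 0.16 = 9.6.

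Case A: the planning variance is net of the other factors. Power of the one-factor model:

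| Effect of each other factor | Added variance | λ | Power at 240 | N needed |
|---|---|---|---|---|
| 0 | 0 | 9.6/1.20 = 8.00 | 80.4% | 238 |
| 0.20 | 0.02 | 9.6/1.22 = 7.87 | 79.8% | 242 |
| 0.40 | 0.08 | 9.6/1.28 = 7.50 | 77.9% | 254 |

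A joint model stays at about 80.4% in every row.

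Case B: the planning variance already contains the other factors. The one-factor model has λ = 8.00 and 80.4%. The joint model removes 0.02 or 0.08: 9.6/1.18 = 8.14 gives 81.1%, and 9.6/1.12 = 8.57 gives 83.0%.

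**Interaction step, read literally.** Take factors A and B in balanced cells, no true interaction, and a true effect e of B. The cell means are 0 (both OFF), e (B only), 0 (A only) and e (both). Fit intercept, A and A×B without B, coded 1/0. The A-OFF cells share one fitted mean, e/2. The A-only cell gives e/2 + a = 0, so a = −e/2. The cell with both ON gives e/2 − e/2 + ab = e, so ab = e. The product term reports an interaction of size e where there is none. With −1/2, +1/2 coding and equal cells the columns are orthogonal and this does not happen. The protocol states no coding.

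**The case against.** A reader might infer that 240 retained no longer gives the stated 80% power. The documents do not support that as a fact. The protocol states no effect size and does not say that its variance excludes the other factors. A plain ON/OFF slope contrast, which is the model described, is consistent with 238, so the variance may already be marginal (Case B). The stated margin is only about 0.4 points, so almost any change of assumption crosses 80%.

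The ratio of 1 is also a floor. With δ held at 0.40, a ratio of 1.5 gives V = 0.133, and full-size omitted effects give λ = 9.6/(1.133 + 0.08) = 7.91, or 80.0% power. That stands, with one qualification: the relief comes from having more power than 238 implies. If δ is instead re-solved so that 238 is still the answer, (1 + V)/δ² stays at 1.20/0.16 = 7.5, and λ with equal effects omitted is 60/(7.5 + 0.5) = 7.5 at any ratio. In addition, counting only 240 treats dropouts as contributing nothing, whereas likelihood-based estimation uses their partial data.

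A second tempting inference is that the main effects lose most of their precision because they would be read from an interaction model coded 1/0. The protocol tests main effects before the interaction step, calls that step exploratory, and states no coding. Adding higher-order terms can also fairly be read as bringing the lower-order terms with them.

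A third is that the factor estimates are biased or the allocation is faulty. Assignment is randomized with half ON on each factor, so chance imbalance between factors costs precision but is not systematic bias. The protocol does not say that the minimization ignores the eight arms.

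**Conclusion.** The analysis wording does not match the design and should be changed, but this is an efficiency and clarity point rather than a demonstrated power failure or a source of bias. With δ = 0.40 slope SD (assumed), a ratio of 1, equal spacing and a two-sided test, one-factor models lose between nothing and about 2.5 points of power at 240, depending on whether the other factors have no effect or the full design effect. If the planning variance was already marginal, the stated 80% is kept, and joint modelling gains about 0.7 to 2.6 points (81.1% or 83.0% against 80.4%). In every scenario computed the joint model does at least as well, so the recommendation does not depend on which case applies.

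The interaction point rests on a literal reading and matters under 1/0 coding. Since the protocol settles neither the coding nor the lower-order terms, it should do so.

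**What to change.** For each outcome (weight, physical activity, calorie intake), replace the three models with one that contains time × Coach Share, time × Group Share and time × Friend/Family Share together, each factor coded −1/2 and +1/2. For the exploratory question, add the two-way and then the three-way interactions with time to that same model, keeping all lower-order terms. Keep the main-effect tests on the effect-coded terms. Use the joint model as the base for the Aim 3 moderator analyses.

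The cost is a sentence or two in the protocol, and two more time-by-factor terms in a model on 320 people. No new data are needed, and this point calls for no change to the randomization. If a statistical analysis plan already fits the factors jointly, the protocol wording only needs to be brought into line. It would also help to state the effect size behind 238 and whether the assumed slope variance includes the other two factors.

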person, with adaptation in wording as needed, yielding scores for each party. Most mediators and the moderator are only measurable once treatment has begun (e.g., coaching quality, social comparison with the LM group, and quality of the relationship with the group cannot be rated at pretreatment). Therefore, the “baseline” administration of such variables will occur at month 3 of treatment, with analyses controlling for weight loss achieved from months 0-3 as appropriate.

Qualitative data

Semi-structured interviews ($n = 30$) will be conducted at post-treatment to gather qualitative information about index participant experiences. 30 of the 320 index participants will be randomly selected with representation across conditions, age, sex, and race/ethnicity; additional interviews will be conducted if saturation is not reached. Interviews will last 45-60 minutes and will be digitally recorded and transcribed verbatim.

Optional Ecological Momentary Assessment- Wave 1 Only

Wave 1 participants *only* will have the opportunity to take part in a five-day ecological momentary assessment (EMA) to learn more about participants’ thoughts and feelings about self-monitoring their weight, their weight loss trajectory in the program so far, and whether these responses differ by treatment condition (i.e., based on which sources of support they have been sharing their self-monitoring data with). Participants will be paid an additional \$75 for completing this optional assessment and will lose \$3 for every survey they do not complete.

Wave 1 participants will be verbally informed about the opportunity to complete the optional additional assessment by their coaches. All Wave 1 participants will be emailed a revised informed consent through RedCap that includes the information on this additional assessment. All participants will digitally read and submit and revised informed consent. After, they will indicate whether or not they would like to opt-in to the study. Those who do not want to participate will exit the RedCap survey. Those who do want to participate will be asked to complete a 5-minute survey that asks about their overall satisfaction with weight loss so far, their lowest weight during the program, and their current weight loss goals (maintain, lose a little more, lose a lot).

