Analyses will determine if change in potential mediators from baseline to 12 months predict weight loss at 24 months. Analyses will determine whether temporally precedent changes in hypothesized mediators explain the effect of condition on weight loss, with the expectation that the Share ON participants will maintain a high level of the proposed mediator from baseline to 12 months, while decreases in that variable will be observed in Share OFF. Coach Share, Group Share, and Friend/Family Share will each be examined separately, with possible mediators including perceived supportive accountability, motivation, self-regulation, and self-monitoring. In addition, coaching quality will be examined as a mediator for Coach Share ON vs. OFF, social comparison will be examined as a mediator for Group Share ON vs. OFF, and perceived social support will be examined as a mediator for Friend/Family Share ON vs. OFF. We will use the mediation model outlined by Preacher and Hayes to estimate the indirect effect of each hypothesized mediator individually. The bias-corrected bootstrap test will be applied to test the significance of the indirect effect, which allows for the most robust and accurate interpretation of the mediating effects. Should these mediation analyses prove promising, we will explore how the entire pattern of changes in the mediators from baseline to later time periods influences the corresponding pattern of weight loss over time using parallel process growth models.

Aim 3

To test if intervention effects depend on quality of the relationship with the coach, group members, or friend/family member, relationship quality will be examined as a potential moderator by adding it to the multilevel model described in Aim 1 and determining whether the effect of condition on change in weight depends on this variable. Relationship quality will be examined at baseline, and also will be examined separately at 6 and 12 months (controlling for weight loss up to that point). Statistically significant interactions will be interpreted by plotting simple regression lines for high and low values of this variable. To analyze qualitative data, transcribed interviews will be coded for thematic analysis. Coding steps will include the development of preliminary themes,

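### Aim 2 uses change in each mediator from baseline to month 12 without adjusting for the mediator's own baseline; if scored as a plain difference, this costs power and can misstate the indirect effect

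*Protocol*

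**What the plan says.** All references are to the Protocol.

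- **Statistical Analysis, Aim 2**, makes change the mediator twice: "Analyses will determine if change in potential mediators from baseline to 12 months predict weight loss at 24 months", and "Analyses will determine whether temporally precedent changes in hypothesized mediators explain the effect of condition on weight loss".
- The same paragraph fixes the model ("We will use the mediation model outlined by Preacher and Hayes to estimate the indirect effect of each hypothesized mediator individually") and the test ("The bias-corrected bootstrap test will be applied to test the significance of the indirect effect"). It names no covariates. Its stated expectation is that "Share ON participants will maintain a high level of the proposed mediator from baseline to 12 months", with a fall in the OFF group.
- **Procedures, Moderators**, explains that most mediators cannot be rated before treatment begins, so the first "administration of such variables will occur at month 3 of treatment, with analyses controlling for weight loss achieved from months 0-3 as appropriate".
- **Statistical Analysis, opening paragraph**, has the only other covariate rule: "Key baseline variables that differ by condition will be considered for use as covariates in the analyses described below".

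Neither covariate rule puts the mediator's own baseline into the mediation equations as a matter of course. The first concerns early weight loss. The second applies only to variables that happen to differ between conditions, and then only for consideration.

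**The concern.** A mediation analysis multiplies two paths: sharing to mediator, and mediator to weight. A difference score with no baseline covariate affects both.

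- **Sharing to mediator.** The difference carries the noise of two measurements. Adjusting the month-12 value for baseline removes more of that noise.
- **Mediator to weight.** The difference forces the baseline and month-12 values to have equal and opposite effects on weight. If the month-12 level is what matters, its effect is diluted. If the baseline level has its own link to weight, part of that link is charged to the change.

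At stake is the trial's evidence on mechanism. A real mediator could be missed, and in some circumstances an indirect effect could be declared where the month-12 level does nothing. The parallel process growth models do not protect against a miss, because they are planned only if the first mediation results look promising.

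**Working it through.** **The plan's own figure.** The sample size section requires 238 and enrols 320 with up to 25% attrition. 238 / 0.75 = 317.3, so 318, and 320 x 0.75 = 240, which covers 238. The 238 cannot be rebuilt because no effect size is given. It concerns the multilevel weight model; no figure is given for mediation.

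**Inputs.** From the Protocol: 240 remaining, half ON and half OFF (120 each), alpha 0.05. Assumed, because the Protocol gives no values:
- rho, the correlation of baseline with month-12 mediator: 0.3, 0.5, 0.7
- unit variance of the mediator at both times
- a = 0.4 SD, effect of sharing on the mediator
- b = 0.25, effect of the month-12 level on weight loss
- c, the baseline mediator's own effect on weight loss
- k = 0.5, correlation of months 0-3 weight loss with the month-3 mediator.

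**Step 1: sharing to mediator.** Residual variance is 2(1 - rho) for the difference and 1 - rho^2 for the baseline-adjusted month-12 value. The ratio, adjusted to change, is (1 + rho)/2 = 0.65, 0.75, 0.85. Both estimates are unbiased under randomisation if sharing has not yet moved the baseline value. For an assumed effect of 0.363 SD with 120 per group, power is 66% against 84%, 80% against 90%, and 95% against 98% at rho 0.3, 0.5 and 0.7.

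**Step 2: mediator to weight, no covariate.** The coefficient on the difference is (b - c)/2 at any rho. It is b/2 when c = 0, zero when c = b, and equal to b only when c = -b, that is, when weight depends purely on change.

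**Step 3: the same path with early weight loss included.** Given that covariate, the month-3 mediator has variance 1 - k^2 = 0.75. Then:
- variance of the difference, V = 0.75(1 - rho)^2 + (1 - rho^2)
- multiplier on b: [(1 - rho^2) - 0.75 rho(1 - rho)] / V
- multiplier on c: -0.75(1 - rho) / V.

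At rho = 0.5, V = 0.1875 + 0.75 = 0.9375. The multiplier on b is (0.75 - 0.1875)/0.9375 = 0.60, and on c it is -0.375/0.9375 = -0.40. So with c = 0 the indirect effect is 0.4 x 0.25 x 0.60 = 0.06 instead of 0.4 x 0.25 = 0.10. The covariate helps a little (0.60 instead of 0.50) but does not repair the path. The variance ratio of step 1 becomes 0.75/0.9375 = 0.80 instead of 0.75.

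**Step 4: power for the whole indirect effect** (simulated, early weight loss in both equations, c = 0):

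| rho | change | baseline-adjusted |
|---|---|---|
| 0.3 | 54% | 85% |
| 0.5 | 54% | 86% |
| 0.7 | 41% | 78% |

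These rates use a joint test of the two paths. A run with the planned bias-corrected bootstrap, without the covariate, at a = 0.363, b = 0.3 and rho = 0.5, gave 53% against about 92%, so the gap does not come from the choice of test.

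**Step 5: false mediation.** Set b = 0 and a total baseline link to weight of 0.3. If none of that link runs through early weight loss, the expected false indirect effect at rho = 0.5 is 0.4 x (-0.40) x 0.3 = -0.048. Simulated rejection with change:

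| share of the link through early weight loss | rho 0.3 | rho 0.5 | rho 0.7 |
|---|---|---|---|
| none | 43% | 37% | 24% |
| half | 9-14% over the three values | | |
| all | nominal | nominal | nominal |

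If sharing does not move the mediator (a = 0), the change form stays near 6% (bootstrap run without the covariate). With a positive baseline link, the false effect has the opposite sign to the hypothesis.

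**Step 6: equivalence.** Once the mediator's baseline is in both equations, the change and the month-12 value give the same indirect effect (checked: 0.097 both ways).

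Simulated rates carry Monte Carlo error of up to about 2.5 points.

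**The case against.** **The Protocol does not say that change is a raw difference.** A reader might infer that it does, but residualised change is also change, and an analysis plan not shown here could fix the scoring and the covariates. This stands, and the point is therefore conditional. It does not dispose of it: the Protocol names change as the mediator twice, and where it wants an adjustment, as for weight loss in Aim 3, it writes one.

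**The hypothesis is about change as much as level.** The phrase about maintaining a high level might be read as a statement about level alone. The sentence goes on to contrast it with a decline in OFF, so it does not settle whether level or change drives weight. If it is purely change, the unadjusted form is unbiased and adjustment can cost power at high rho. This stands.

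**Early weight loss is a planned covariate.** Without it, calculations give false-mediation rates of 55% and more. A reader might take such figures as the plan's error rate. They are not: the Protocol calls for that covariate as appropriate, and with it the rate runs from nominal to 24-43%. Nor is the indirect effect always halved; it is about 0.6 of its true value under the assumptions above.

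**Baseline is not always clean or available.** Coaching quality is rated on a 15% sample of each coach's work, so a participant-level baseline may not exist. Month 3 falls after randomisation, and coach data access is described as continuous, so month-3 values may already reflect sharing. Both stand as cautions. The second does not favour the difference: if sharing has already moved the month-3 value by s, the difference subtracts all of s, the adjusted form only rho times s.

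**Conclusion.** The point holds in conditional form. Aim 2 makes change from baseline to month 12 the mediator and does not adjust for the mediator's own baseline. If change is a plain difference, precision is lost in the first path whenever rho is below 1, and the second path is correct only if weight depends purely on change.

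The power loss is substantial under the assumed effects, about 30 to 37 points. The false-mediation risk is narrower: it needs a real sharing effect on the mediator and a baseline link to weight beyond early weight loss. All sizes depend on assumed rho, a, b, c, k and equal variances. The Protocol summary describes the mediator work as a secondary, exploratory aim, and the primary weight analysis is untouched.

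**What to change.** In Aim 2, state that for each mediator with a participant-level baseline, that baseline (month 0 or month 3, as applicable) enters both equations alongside months 0-3 weight loss:

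- month-12 mediator on Share, baseline mediator and months 0-3 weight loss;
- 24-month weight loss on Share, month-12 mediator, baseline mediator and months 0-3 weight loss.

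The word change may stay, since with baseline in both equations the two scorings give the same indirect effect. Keep the unadjusted change analysis as a sensitivity analysis. Include coaching quality in this form only if a participant-level baseline rating exists.

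Cost: a sentence of text, one degree of freedom per equation and no new data. If weight depends purely on change and rho is about 0.7, the adjusted form loses about 4-5 points of power.

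### Aim 2 tests each mediator in its own model only, so it cannot separate correlated mediators that data sharing also moves

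*Protocol*

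**What the plan says.** Protocol, Statistical Analysis, Aim 2, states the question as "Analyses will determine if change in potential mediators from baseline to 12 months predict weight loss at 24 months", and asks whether those earlier changes account for the effect of condition on weight. Each Share factor is taken separately, "with possible mediators including perceived supportive accountability, motivation, self-regulation, and self-monitoring". One further candidate is added per factor: "coaching quality will be examined as a mediator for Coach Share ON vs. OFF", with social comparison for Group Share and social support for Friend/Family Share. That makes 4 + 1 = 5 candidates per factor and 15 factor-by-mediator tests.

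The model is fixed: the method is used "to estimate the indirect effect of each hypothesized mediator individually", and "The bias-corrected bootstrap test will be applied to test the significance of the indirect effect". The only follow-up is conditional: "Should these mediation analyses prove promising, we will explore how the entire pattern of changes in the mediators" relates to the pattern of weight loss, using parallel process growth models. The section describes no model that holds one mediator constant while testing another.

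The same section expects Share ON participants to hold a high level of the proposed mediator to month 12 while Share OFF participants decline. The Protocol's opening summary describes the mediator aim as exploratory; the Objectives section words it as a test.

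**The concern.** Randomisation protects the path from sharing to a mediator. It does not protect the path from the mediator to weight. Supportive accountability, motivation, self-regulation, self-monitoring and social support are related constructs. In a one-mediator model, any correlated mediator left out confounds the mediator-to-weight coefficient. If sharing also shifts the tested variable, the product of the two paths is non-zero even when that variable does nothing to weight.

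At stake is what Aim 2 can be used for. A significant single-mediator result is compatible with that variable being the mechanism, and equally with its travelling alongside the mechanism. The single tests alone cannot tell accountability from, say, self-monitoring.

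**Working it through.** **Inputs from the Protocol.** 320 index participants, 1:1 ON/OFF for each factor, up to 25% attrition: 320 × 0.75 = 240, which covers the stated requirement of 238. The Protocol gives no error rate or power for the mediation tests, so there is no figure to reproduce.

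**Assumed inputs (not in the Protocol).** Two mediators with unit residual variance and residual correlation ρ. Sharing shifts the true mediator M1 by a1 and the inert mediator M2 by a2. Only M1 affects weight, by b SD per SD, with residual SD 1. Two-sided 5% level.

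**What the single model estimates for M2.** With M1 omitted, the coefficient of weight on M2 is b × ρ, so the apparent indirect effect is a2 × b × ρ. With a2 = 0.4, b = 0.3, ρ = 0.5 this is 0.4 × 0.3 × 0.5 = 0.06, half of the true mediator's 0.4 × 0.3 = 0.12. It is zero if a2 = 0.

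**How often that is declared significant.** As an approximation, both paths must be significant.
- Path a: SE = 2/√240 = 0.129; z = 0.4/0.129 = 3.10; probability 0.873.
- Path b for M2 alone: SE = √[(1 + b²(1 − ρ²))/240]. For b = 0.3, ρ = 0.5: √(1.0675/240) = 0.0667; z = 0.15/0.0667 = 2.25; probability 0.614.
- Product: 0.873 × 0.614 = 0.54.

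| ρ | approximation, b = 0.3 / 0.4 | simulated, M2 alone, b = 0.3–0.4 | simulated, M2 with M1 in the model |
|---|---|---|---|
| 0.3 | 23% / 36% | 23–35% | 3–5% |
| 0.5 | 54% / 73% | 49–71% | 3–5% |
| 0.6 | 68% / 82% | 67–81% | 3–5% |

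The simulations use a Monte Carlo interval for the product. Separate runs agree within a few points.

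**Correlation without a shift (a2 = 0).** The product is 0.05 × P(path b significant), which cannot exceed 5%; in the example, 0.05 × 0.614 = 3%. Simulation gave about 1–3%.

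**With the planned bias-corrected bootstrap** (n = 240, a1 = 0.36, b = 0.3; ρ = 0.3, 0.5, 0.7):
- Equal shift (a2 = a1): 31%, 61%, 79%.
- Shift proportional to the correlation (a2 = ρ × a1): 6%, 29%, 55%.
- No shift: 2–7% in the 1,000-trial settings, and up to 12% in the noisier 300-trial ones.
- M2 with M1 in the model: about 1–9% over all settings.

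Over a wider grid (n = 240 and 320, a1 = 0.2–0.5, b = 0.3–0.4, ρ = 0.3–0.7), the single-model rate was 20–96% with equal shifts and 6–83% with proportional shifts.

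**Cost of a joint model.** With two mediators, power for the true one was 86–88% alone and 82–88% jointly. With five, it went from 87% to 86%, 87% to 80% and 89% to 78% at ρ = 0.3, 0.5 and 0.6.

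**Limit of a joint model.** For a chain from sharing to accountability to self-monitoring to weight (a = 0.5, b = 0.4, link 0.5–0.7), accountability is a genuine mediator. It was detected in about 79–96% of trials alone but only about 5% in the joint model.

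**The case against.** The strongest reply is that the Protocol claims less than the concern supposes. It speaks of possible and potential mediators, its summary calls the aim exploratory, and it nowhere says that a significant single test shows a unique pathway. An SAP, not shown here, could add a joint model. This stands as a reason to call the point an improvement to a secondary aim. It does not remove it: the Protocol fixes the one-at-a-time model explicitly, and its only follow-up is conditional and does not adjust one mediator for another.

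A second reply is that a joint model can mislead too. That also stands. The chain example shows a real upstream mediator almost always losing its specific effect. A chain is plausible here, because support partners are trained to respond to shared data in ways that build motivation and self-regulation. A rule that recognises a mechanism only when the joint model supports it would therefore be unsound.

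Two stronger readings are tempting. A reader might infer that correlation with the true mediator is enough by itself. It is not: without a shift from sharing, the rate stays near nominal. A reader might also infer that Aim 2 will find that every candidate works. That does not follow for any mediator that sharing leaves unmoved.

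**Conclusion.** The concern holds in this form: single-mediator tests cannot separate correlated mediators that sharing also moves, and the Protocol names no other model that could. Both conditions are plausible on the Protocol's own account, since the constructs are related and ON/OFF separation is expected on each.

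The direction follows from a2 × b × ρ whenever all three terms are non-zero. The size does not follow from the Protocol. The rates of 23–35%, 49–71% and 67–81% illustrate equal 0.4 SD shifts, b of 0.3–0.4 and correlations of 0.3, 0.5 and 0.6. Other reasonable inputs give anything from about 6% to 96%, so no single percentage should be quoted as a property of this trial. The 3–5% for the joint model assumes that the true mediator is among those measured and included. The primary weight analysis is unaffected.

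**What to change.** In the Aim 2 analysis section or the SAP:

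1. Keep the planned single-mediator analyses, reported as total indirect effects, with a statement that they do not distinguish among correlated mediators.
2. For each Share factor, add one multiple-mediator model containing its participant-level mediators, and report the specific indirect effects. Coaching quality is rated on a 15% sample of each coach's contacts, so it may not be available as a participant-level variable.
3. Where one mediator is thought to act through another, such as accountability through self-monitoring, state the order in advance and report the serial path.
4. State that a mediator is not rejected solely because its specific effect vanishes in the joint model.

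No new data are needed. The cost is one more model per factor and wider intervals for the specific effects, about 0–10 points of power with five mediators under the assumptions above.
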